- 3) **Referral** to a higher level facility if: a) BP≥140/90 mmHg and aged<40 or already medicated with at least one drug; b) known heart disease, stroke, TIA, diabetes, kidney disease, angina, claudication or worsening heart failure; c) certain cases of high blood sugar; or d) any proteinuria.
- 4) **Prediction** of ten-year risk of fatal or non-fatal CVD event using World Health Organization/International Society of Hypertension (WHO/ISH) risk chart (with or without measure of cholesterol) for those not referred at Action 3.
- 5) **Treatment**: Both individual risk factors and the total CVD risk score are used in prescribing the treatment response (see Appendix A). Those exposed to particularly high risk through a single risk factor (hypertension, pre-existing CVD, high cholesterol and diabetes) should be prescribed the appropriate medication. Those with the CVD risk above 30% are to be given an antihypertensive if blood pressure is elevated and also a statin. Those with CVD risk 20-30% are to be given a low dose antihypertensive. Those with risk below 20%, as all others, are to be counselled on diet, physical activity and smoking cessation. The stipulated frequency of periodic follow-up depends on the risk score.

Department of Health (DOH) monitoring of PhilPEN implementation in six regions in 2015 revealed that not all facilities were following the protocol. Implementation requires that health facilities have sufficient supplies of medications, test devices and materials. The monitoring did not assess the availability of devices and materials at health centers but interviews conducted by the study team in Rizal and Pampanga provinces revealed that many RHUs are unable to perform blood tests and must refer patients to higher level facilities, which can result in the test not being undertaken.

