Kariuki et al (2013) evaluate the performance of the WHO/ISH charts against criteria for a clinically useful CVD risk assessment (Cooney et al, 2009). The algorithm is found lacking with respect to representativeness of sample (which is entirely lacking), appropriateness of statistical methods (not specified) and checks on internal and external validity (not conducted). Selvarajah et al (2014) demonstrate that even the chart that makes use of information on cholesterol performs poorly in predicting CVD risks in the Malaysian population, with gross underestimation of risk. Despite the study sample having high prevalence of risk factors, the WHO/ISH risk chart placed 90% in the low-risk category (10-year CVD risk <10%), while the non-laboratory Framingham algorithm (D'Agostino, 2008), which uses BMI instead of cholesterol, categorized only 48% as low risk. The WHO/ISH chart placed only 3% in a high-risk category (10-year CVD risk >30%), while Framingham placed 23% in this category (10-year CVD risk \geq 20%). In addition to low agreement on risk categorization, there was low correlation between WHO/ISH and both the Framingham and the SCORE algorithms. The low correlation was due to the WHO/ISH charts placing many at low risk that the other two algorithms classified as high. The tendency for WHO/ISH charts to categorize the vast majority in the low risk category despite high prevalence of CVD risk factors has been demonstrated for Cambodia (97%) (Dugee et al 2013), Cuba (90%) (Nordet et al 2013), Jamaica (89%) (Tullock-Reid et al 2013) and Mongolia (94%) (Dugee et al 2013). Accuracy of the charts, particularly whether the risk classification is sufficiently detailed for medium to high risks, has been questioned (Persson et al 2003; Yikona et al 2002).

The apparent downward bias in risk prediction using the WHO/ISH charts means that the PEN, in the Philippines and elsewhere, may well be failing to deliver primary prevention of CVD to many who could benefit from it. One objective of this study is to examine whether this is indeed the case.

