Individuals may be apprehensive of utilizing their beliefs about CVD risk because they lack confidence in the accuracy of those beliefs. Their beliefs are ambiguous. If individuals are ambiguity seeking in the loss domain, which is often found (Dimmock et al 2015), and are informed that their risks are lower than they had reported, then on gaining confidence in their downwardly revised beliefs they may become responsive to them. Being surer that the CVD risk is 15% rather than being very uncertain that it is 20% may cause an individual to adopt healthier behaviour.

Test:

• Repeat the regressions of the previous test but rather than including a single indicator of treatment group enter two indicators. One identifies respondents in the treatment group informed that their risk is above their initially reported risk. The other identifies respondents in the treatment group informed that their risk is at or below their reported risk. If it is only the correction of bias in risk perceptions that affects behaviour, then only the first group should adopt healthier behaviour. The second group, if anything, should adopt less healthy behaviour. If, to the contrary, the second group responds to the positive news they are given of their CVD risk by adopting healthier habits, this suggests an effect through reduced ambiguity. In addition, we will examine how the provision of information affects stated confidence in individuals' estimates of their risks of heart attack/stroke.

Q6: Is PhilPEN effective in delivering primary prevention of CVD to those who seek care at RHU/CHCs?

[H6a] As currently implemented, PhilPEN does not reduce the risk factor exposure and increase the medication of individuals with elevated CVD risk.

Test:

- Induce random variation in presentation for checkup at RHU/CHCs, which under PhilPEN are required to conduct CVD risk assessment of all patients, to screen those meeting specified criterion, to counsel all those screened on smoking cessation and to provide hypertension and diabetes medication to those at high risk defined by the WHO PEN protocol.
- The information intervention will not be used to generate this random variation since beliefs about CVD risk can impact on behaviour directly even without contact with health facilities and the PhilPEN program.

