Finally, a treatment group respondent will receive information on what the 10-year CVD risk would be for someone of the same age and gender who did not smoke, and had normal blood pressure and BMI. This will be presented as the optimal risk that could be achieved through primary prevention. If the respondent's risk is above the optimal, then they will be told the reason(s) for this - smoking, above a healthy weight or blood pressure reading is above normal. And the respondent will be told how the risk could be reduced – quit smoking, lose weight, get blood pressure down by taking medication, exercising, losing weight, eating less salt and fat. If the respondent's risk is not above the optimal, then they will be congratulated and advised how to keep the risk low.

CVD risk prediction algorithm

We have several reasons for not using the WHO/ISH risk charts to predict 10-year CVD risk, despite their use in PhilPEN. First, there are the methodological weaknesses of these charts identified in Section 2. They appear to produce downwardly biased predictions of CVD risk, which would result in less variation within the treatment group in the information on CVD risk provided. Besides providing inaccurate information and missing much of the variation in actual risk, we would need a much larger sample size in order to identify the effect of the intervention. It would hardly be worthwhile to randomize to a treatment if there is no variation in that treatment for 90% of the treated.

Further, the WHO/ISH charts only allow categorization of individuals into five ranges of CVD risk. They do not provide a point estimate of the CVD risk for each individual. This would have two drawbacks for our study. First, it would further limit the variation in the information we would be able to provide in the intervention. Second, it would not allow us to test the extent to which individuals use the information provided to update their reported estimate of the CVD risk.

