5.3 Lottery incentive for CVD risk assessment

The goal of the second intervention is to evaluate the effectiveness of the PhilPEN program in delivering primary prevention of CVD. This will be achieved by offering randomly selected respondents a ticket for a lottery with a money prize on condition that they visit a RHU/CHC for a checkup. There will be one prize per barangay giving each respondent a one in ten chances of winning P5000 (US\$100). The prize is equivalent to approximately 14 days earnings at the regional minimum wage⁵. This *randomized encouragement design* will induce exogenous variation in patients accessing the PhilPEN program allowing its impact to be estimated.

As noted in Section 3.1, there are potential weaknesses in implementation of the PhilPEN program and the purpose of this component of the experiment is to establish the effectiveness of the program as it is currently implemented. For that reason, there is no supply-side component to the intervention. Respondents will simply be told that they can enter a lottery if they go to the RHU/CHC for a checkup. The health facilities will be told to conduct an assessment deemed appropriate for any particular patient that requests to be issued with a lottery ticket. No instructions will be given that the facilities should follow the PhilPEN protocol. We will evaluate whether they do implement the protocol for patients who qualify (by age if nothing else) for full risk screening.

The remainder of this sub-section describes the logistics of the lottery intervention.

Designating a RHU/CHC point person. The agreement will state that the MHO/CHO should designate a point person in the RHU/CHC facility who will be responsible for handing out the lottery tickets. This should be one of the medical staff (e.g. the rural health nurse, midwife or the MHO/CHO, or PhilPEN coordinator) who performs or delegates the performance of the PhilPEN profiling and screening. The identity of this point person will be included in the information provided by enumerators to the lottery recipients.

Voucher and ticket. A voucher will be given by the enumerator to those deemed eligible for the lottery intervention at the end of the interview. This voucher will be surrendered at the facility to the RHU/CHC point person in exchange for a lottery ticket. The voucher and ticket will both be pre-numbered with the same number.

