UPecon survey												Х	Х		
monitoring															
Survey firm delivers														Х	
follow-up data															
Analysis of follow-up data														Х	Х
Write papers															\rightarrow

Our intention is to field the baseline survey in August-September 2017. As explained above, the information intervention will form part of the risk perceptions module of the baseline survey. The module used with information treatment group respondents will differ from that used with the lottery treatment group and the control group. The module will be positioned in the survey after physical measurements of blood pressure and BMI in order that these measures can be used in the calculation of the predicted CVD risk that will be revealed to the treatment group respondents.

Those allocated to the lottery intervention will be told of their chance to enter the lottery at the end of the baseline survey and given a voucher to be exchanged for a lottery ticket at a specific RHU/CHC. The chance to enter the lottery expires one month after the baseline in order that we observe a sufficiently long period between risk assessment at the designated facility and the follow-up survey.

The follow-up will be conducted around 6-7 months after the baseline in March-April 2018. This will provide sufficient time to observe the effect of medications prescribed at initial contact with the RHU/CHC and to assess whether follow-up consultations are conducted for the target populations, as stipulated by the PhilPEN protocol.

7. Outcomes

We will estimate effects on predicted CVD risk, risk factors, health care management of CVD, CVD-related behaviours, perceptions of CVD risk and knowledge of CVD risk factors.

Principal outcome

The principal outcome for both interventions is mean 10-year risk of a heart attack or stroke predicted using the office version of Globorisk (Udea et al 2017).

i) Mean 10-year risk of CVD event (Globorisk prediction)

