The information intervention may impact on this outcome through multiple mechanisms. Individuals who are made aware that the CVD risk for individuals with their risk factor profile is higher than they had anticipated, who are provoked to recognize that they face a non-negligible risk without having given serious thought to this risk previously and who are told by how much the risk could be reduced by quitting smoking, reducing blood pressure, losing weight etc, may be provoked to take actions to reduce their risk. Actions could include: going for a checkup at a RHU/CHC or other health facility with the possibility of subsequently being put on medication for hypertension, diabetes or high cholesterol, attempting to lose weight through diet and/or exercise, and quitting smoking. Any efforts that are

effective in reducing blood pressure, reducing weight and stopping smoking will translate into a reduced 10-year CVD risk score.

The lottery intervention may impact on the predicted 10-year CVD risk by inducing respondents to attend a RHU/CHC where they can access PhilPEN risk assessment. Given the age criterion for inclusion in the study (40+), according to the protocol all those attending a RHU/CHC should be subject to PhilPEN risk screening, which includes tests for blood glucose, urine protein and cholesterol, in addition to measures of blood pressure and weight taken in risk assessment. All those screened should be given counselling on smoking cessation, diet and exercise. Those with sufficiently high risk, should be given medication for hypertension and/or diabetes, which are supplied to RHU/CHCs by the department of health. According to the protocol, those with sufficiently high risk should also be given statins, although these are not supplied by the department of health.

The proportion of the population with elevated CVD risk is likely to be more important for population health than is the mean risk. Unfortunately, we do not have data that allow us to estimate the proportion with elevated risk predicted by the Globorisk algorithm. Hence, we cannot conduct power calculations for this outcome. However, we intend to estimate the impact on it providing that an ex-post calculation confirms that there is sufficient power. We will estimate effects on:

ii) Proportion with 10-year CVD risk (Globorisk prediction) $\geq \tau\%$

The threshold (τ) for elevated CVD risk will be set at 10%, and if there proves to be sufficient power, also 20% and 30%.

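### The plan sets out to examine whether WHO/ISH under-prediction makes PhilPEN miss people who could benefit, but no analysis uses a WHO/ISH band, so non-treatment that depends on the chart cannot be explained

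*Combined protocol and SAP*

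**What the plan says.** Section 3.1 (Primary prevention of CVD through the PEN) reviews evidence that the WHO/ISH charts under-predict. It infers that the PEN "may well be failing to deliver primary prevention of CVD to many who could benefit from it" and continues: "One objective of this study is to examine whether this is indeed the case".

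The analysis sections use a different score. Section 5.2 states: "We have several reasons for not using the WHO/ISH risk charts to predict 10-year CVD risk, despite their use in PhilPEN". Section 7 states: "The principal outcome for both interventions is mean 10-year risk of a heart attack or stroke predicted using the office version of Globorisk". For elevated risk, also scored by Globorisk, it says "The threshold (τ) for elevated CVD risk will be set at 10" per cent, with 20% and 30% added if power allows.

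Under H6a, Section 3.2 describes facilities as required "to provide hypertension and diabetes medication to those at high risk defined by the WHO PEN protocol". No test identifies that group.

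The plan does intend to look at delivery. Section 5.3 says: "We will evaluate whether they do implement the protocol for patients who qualify". Section 7 lists advice and counselling outcomes xii to xviii, conditional on an ex-post power check. It also plans to monitor tests, advice and medication among attenders. The task sheet for the facility point person asks for a note of the assessments and procedures done; the text available does not ask for the WHO/ISH category assigned.

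**The concern.** Facilities allocate chart-dependent treatment on WHO/ISH, while the trial scores risk on Globorisk. If medication barely rises among people induced to attend, there are two explanations. Either the protocol was followed and the chart placed people below its medication bands, or the protocol was not followed (or stock was missing). The first points to the risk tool, the second to delivery.

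Section 3.1 promises to distinguish scenarios, but the one it names for a failing programme is poor operation within facilities. Without a WHO/ISH band in the analysis, non-treatment caused by the chart could be reported as a facility failure, and the question about the chart would stay unanswered.

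**Working it through.** **1. Is a WHO/ISH band used anywhere?** Hypotheses H1a to H6e, outcomes i to xxi and the regressions in Section 3.2 use Globorisk, individual risk factors, beliefs, attendance, medication or advice. None uses a WHO/ISH score or band as outcome, covariate or subgroup.

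**2. Where does the chart decide medication?** The sample is aged 40 to 70, reports no diabetes, heart disease or stroke, and is not taking antihypertensives at baseline (Section 9). The blood pressure referral rule in Section 2 covers people under 40 or already medicated, so it largely does not apply. For antihypertensives, Appendix A then reads:

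| Blood pressure (mmHg) | WHO/ISH <20% | 20 to <30% | ≥30% |
|---|---|---|---|
| ≥160/100 | medication | medication | medication |
| ≥140/90, below 160/100 | counselling | medication | medication |
| ≥130/80, below 140/90 | counselling | counselling | medication |
| below 130/80 | counselling | counselling | counselling |

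The chart matters only in the two middle rows, and only from 20% upwards. Counselling is prescribed in every risk band.

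**3. What can the planned data separate?**
- Low attendance: yes, through H6b.
- Missing tests or counselling: yes, through Section 7 monitoring, outcomes xii to xviii and the facility notes.
- Non-treatment at ≥160/100: yes, with no chart score needed.
- Non-treatment in the two middle rows: no. Outcome xi (antihypertensive use) records the same value whether the chart score was below threshold or the protocol was not followed.

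**4. How many people are involved?** The documents do not give the joint distribution of WHO/ISH band, Globorisk and blood pressure, so the number cannot be computed. Two illustrations, both before any blood pressure condition, show how uncertain it is.
- *People whom Globorisk would add.* Substituting Globorisk in Appendix A can add someone only at Globorisk ≥20%. Section 10.1 gives a mean of 11.35% and an SD of one fifth of that, 2.27. Assuming normality, z = (20 − 11.35)/2.27 = 3.81, a share of about 0.01%, or fewer than one of the 1,361 per arm in Table 6 (binary outcomes). Section 10.1 itself cautions about this SD. With an assumed SD of 6, z = 8.65/6 = 1.44, a share of about 7.5%, or roughly 100 of 1,361.
- *People whom WHO/ISH would reach.* In the Malaysian sample cited in Section 3.1, 90% were below 10% and 3% above 30%, so the share at ≥20% lies between 3% and 10%. If 60% compliance is read as attendance, attenders number 0.6 × 1,361 = 817, giving 25 to 82 people. This assumes that shares from another country, using a chart with cholesterol, carry over.

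**5. Can the present sample support the added tables?** Design effect = 1 + (10 − 1) × 0.1 = 1.9. With 3,021 respondents, a 10% cell has a 95% half-width of 1.96 × √(0.10 × 0.90 × 1.9/3,021) = 0.015, or 1.5 percentage points. The sample size is not in dispute. For mean CVD risk the planned effect is 0.2 × 0.6 = 0.12 SD, which needs 1,091 per arm unclustered (two-sided 5%, 80% power). Then 1,091 × 1.9 × (1 − 0.36) = 1,327, against 1,306 in Table 6, within 2%.

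**The case against.** **The headline objectives do not mention the chart.** Section 3.1 opens with two objectives: beliefs and demand, and PhilPEN's effectiveness as implemented. The chart is part of the programme as implemented, and H6a estimates the total effect of a checkup without needing a WHO/ISH score. That stands for the main estimand. It does not dispose of the point: the later sentence is an explicit objective, it follows directly from the argument about chart bias, and no analysis is attached to it.

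**Delivery is measured.** A reader might infer that a null lottery effect could not be attributed to the chart or to poor delivery at all, or that a patient handled correctly but left unmedicated looks identical in the data to a neglected one. The documents do not support either reading. A patient handled under Appendix A should have screening and counselling on record, and the first three items in step 3 of the working are readable without the chart. Only chart-dependent medication is left unexplained.

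**Size.** A reader might subtract the cited low-risk shares (90% on WHO/ISH, 48% on Framingham), obtain 42 percentage points, and apply that to each arm. This is not supported. The comparison is in an external sample, with Framingham rather than Globorisk, and with a chart that uses cholesterol. It also concerns the low-risk band, whereas Appendix A gives counselling both below 10% and from 10% to below 20%; chart-triggered medication starts at 20% and, for antihypertensives, also needs a blood pressure condition.

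**The derived band may differ from the one applied.** Facilities may use glucose, lipids and another blood pressure reading. Setting diabetes to absent would understate WHO/ISH risk for anyone undiagnosed, as Section 5.2 itself notes, and would enlarge the apparent chart gap. This stands, and limits interpretation.

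**Not checkable.** The questionnaire (Appendix C) is not in the text reviewed, so it may ask about a facility-assigned category. Even then, no planned analysis uses one.

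**Conclusion.** The concern holds in a limited form. Followed exactly, the plan cannot answer its stated question about the WHO/ISH charts. For medication that depends on the chart, it cannot separate a score below the treatment threshold from a protocol that was not followed. It can still detect poor delivery in testing, in counselling and at blood pressure of 160/100 mmHg or above.

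The size is not known. Depending on the assumed spread of Globorisk, the people whom it would add at 20% range from fewer than one to roughly 100 per arm before the blood pressure condition. The conclusion itself does not depend on these figures. It rests on Appendix A as printed and on the absence of WHO/ISH from the hypotheses, outcomes and models. The principal analysis and the sample size are unaffected. The change is worth making before follow-up data are seen.

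**What to change.** 1. Derive the no-cholesterol WHO/ISH band at baseline for every respondent. The chart inputs are assumed to be age, sex, smoking, systolic blood pressure and no reported diabetes; all are collected or fixed by eligibility. Cross-tabulate it with Globorisk at 10%, 20% and 30%.
2. As a secondary descriptive analysis, apply the existing Appendix A antihypertensive criteria twice, once with the WHO/ISH band and once with Globorisk in its place. This only classifies records; it does not propose a treatment rule. Among lottery attenders not on antihypertensives at follow-up, report: (a) indicated under WHO/ISH but not given, a delivery gap that includes lack of stock; (b) indicated only when Globorisk replaces WHO/ISH, a chart gap; (c) indicated under neither. Group (c) keeps people whom neither score would bring to medication out of the chart gap.
3. Lottery-versus-control estimates of outcomes i, iii and xi within the baseline-defined groups may be added, labelled secondary and low in precision. These groups preserve the randomised comparison; the split among attenders does not.
4. Before coding, the sponsor should reconcile Section 2 with Appendix A. Section 2 gives no blood pressure condition for antihypertensives at 20 to 30% risk, while Appendix A does.
5. State the limits: undiagnosed diabetes is set to absent, and facilities may use glucose, lipids and a different blood pressure reading, so the derived band may not be the one applied.

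The cost is one derived variable and a few tables, with no added sample or visit. If the sponsor prefers not to do this, the objective in Section 3.1 should be withdrawn or reworded so that it does not promise an answer about the chart.
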